8.4 Exclusion Criteria

Each potential patient must be screened to ensure they do not meet any of the following exclusion criteria. This screening is based on known medical history and data available at the time of eligibility determination and enrollment.

1. Significant disease of the ipsilateral common carotid artery on routine CTA
2. Presence of a cervical ICA loop or other high-risk anatomical features of the ICA on routine CTA, that may preclude the use of the NOVIS NPS
3. Any active or recent hemorrhage within the past 30 days
4. Embolectomy contraindications
 - a. Pre-stroke mRS ≥ 2
 - b. NIHSS ≤ 5
 - c. ASPECTS ≤ 5
5. IV tPA has been or is being administered
6. Last known well > 24 hours ago
7. Known history of severe head injury within past 90 days with residual neurological deficit, as determined by medical history
8. Patient has an isolated hemisphere, defined as intracranial circulation that is fed only by the ipsilateral internal carotid artery and may be detected on prior CTA
9. Known history of neurological or psychiatric disease that would confound the neurological or functional evaluations, e.g., dementia with prescribed anti-cholinesterase inhibitor (e.g., Aricept)
10. Presumed septic embolus, suspicion of bacterial endocarditis or cerebral vasculitis
11. Known history of ipsilateral severe intracranial atherosclerotic disease ($\geq 70\%$ stenosis) documented on prior imaging
12. Patient is known to have an active COVID-19 infection
13. Female who is pregnant or lactating at time of admission
14. Current participation in another investigational drug or device study.
15. Evidence of any other disease or condition expected to compromise survival or ability to complete the endovascular procedure or follow-up assessments during the 90-day follow-up period (e.g. methamphetamine, cocaine, or other recreational drug use)
16. Patient has recurrent or metastatic malignancy or cancer
17. Known history of hemorrhagic diathesis or coagulation factor deficiency
18. Known risks for paradoxical embolism, including intracardiac right-to left shunt (e.g., PFO, ASD, VSD) or history of pulmonary embolism or deep vein thrombosis
19. Patients that have undergone a transradial or transbrachial mechanical thrombectomy attempt prior to enrollment

9 Patient Enrollment

A patient is considered enrolled after:

- 1) written informed consent is obtained,
- 2) meeting all inclusion and none of the exclusion criteria,
- 3) failed transfemoral therapy

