10.3.3 Establishment of Transcarotid Flow Reversal

The type of anesthesia used during the procedure is left to the discretion of the Investigator and will be documented on the CRFs. Should the investigator choose to start with moderate sedation conversion to general anesthetic should only occur if the Investigator deems it necessary. The type of anesthesia used will be documented in the CRFs.

After completing confirmatory duplex ultrasound, access to the common carotid artery cephalad to the clavicle will be gained using surgical techniques.

Investigators are to follow the NOVIS Transcarotid Neuroprotection System (NPS) Instructions for Use (IFU) for setting up and establishing the reverse flow circuit. Upon placement of the NOVIS system and prior to clamping the CCA, the differential in pressure causes some blood to flow between the CCA and femoral vein. At this point, there is still some antegrade flow in the CCA and therefore the carotid and cerebral vasculature is not “protected”. Once the CCA is clamped below the arterial sheath of the system on the Low flow setting, the NPS should remain on Low flow setting and switch to High flow upon the introduction of interventional tools through the completion of the procedure. Upon initial set-up of the device a pressurized, heparinized saline drip is connected to the 3-way stopcock on the side arm of the rotating hemostasis valve.

Any adverse events that are observed after establishing reverse flow will be followed through study exit.

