10.3.4 Endovascular Therapy

Patients will be treated with endovascular therapy system(s) (stentriever and/or aspiration catheters) currently cleared by the FDA, under their cleared indications for use, for thrombus removal in patients experiencing an acute ischemic stroke in the anterior circulation due to large vessel occlusion. Investigators will be trained to follow the published instructions for use for the endovascular therapy system used in the procedure. Deviations from the cleared time of usage must be documented as a protocol deviation. Ensure the neurointerventional devices are labeled with an outer diameter that is compatible with the inner diameter of the NOVIS NPS Arterial Sheath and attached rotating hemostasis valve.

These devices will be introduced into the vasculature via the NOVIS NPS Arterial Sheath, during this interventional step the NOVIS NPS will be set to High Flow and remain on this setting until the neurothrombectomy has been completed.

Once the endovascular therapy systems are introduced into the NOVIS NPS Arterial Sheath continuous reverse flow will be maintained throughout the interventional steps, until all other devices are removed and the thrombectomy attempt is complete.

The transcarotid intervention may be abandoned at the discretion of the treating operator. The operator will document reason for failure in patient records and study case report forms.

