2. INTRODUCTION

The purpose of this Statistical Analysis Plan (SAP) is to prospectively outline the methods for analyses for patients with acute ischemic stroke in the anterior circulation due to large vessel occlusion (LVO) who underwent endovascular treatment using the transcarotid approach with flow reversal in this initial feasibility (NITE 1) study using the NOVIS Neuroprotection System (NPS).

The NITE 1 study is a prospective, multi-center, single arm feasibility study for the endovascular treatment of patients with acute ischemic anterior circulation strokes due to large vessel embolic occlusions using the transcarotid approach with flow reversal. Patients enrolled into the NITE 1 study will have failed transfemoral therapy and will be followed immediately from post-op to 90 days. The primary study objective is to establish the feasibility and safety of the NOVIS NPS in the targeted study population, and as such, this SAP will focus on confirming whether the initial safety signal exists from the primary endpoint data.

With FDA's IDE approval of the study design and sample size, the primary safety study endpoints will be numerically compared to existing TCAR data from the ENROUTE NPS clinical program (PROOF and ROADSTER). The functional independence at 90 days will be compared to reference data for acute ischemic stroke (AIS) patients treated with mechanical thrombectomy and the natural history of AIS in those patients who have not received or have failed mechanical thrombectomy, as cited in Section 5. The primary study endpoints for the NITE 1 study include:

- Device-related Serious Adverse Events – vascular complications including dissection, pseudoaneurysm, hematoma, arteriovenous fistula, thrombus formation, embolization and any vascular complication that may be attributed to the device AND requires surgical repair, surgical wound revision, transfusion, etc.
- Other Serious Adverse Events – permanent cranial nerve injury (CNI), new symptomatic intracranial hemorrhage (SICH) and dissections related to ancillary devices
- Functional independence at 90 days (proportion with mRS score 0-2)

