Serious Adverse Events will be tabulated and reported accordingly. The primary endpoint and all secondary endpoints will be analyzed based on both the ITT and PP population. All available data on the ITT patients who were enrolled in the study will be included. This SAP presents the data results to be reviewed in evaluating the device-related SAEs, other SAEs, and functional independence at 90 days. Secondary endpoints to be summarized include the following:

- Carotid access time
 - Hospital arrival to neck incision
 - Neck incision to carotid exposure
 - Neck incision to carotid artery catheterization (includes securement of sheath)
 - Neck incision to femoral venous sheath access (includes securement of sheath)
 - Neck incision to initiation of reverse flow
- Time to final revascularization
 - Hospital arrival to OR
 - Last known well to final revascularization

- Admission to final revascularization
- OR to final revascularization
- Cutdown to final revascularization
- Arterial introduction of interventional tools to final revascularization
- Total reverse flow time (CCA clamp to CCA unclamp)
- Device-related complications
- Neurologic assessment at 90 days (proportion of patients with a nondisabling or disabling stroke according to NIHSS)
- Technical success rate – Successful introduction of endovascular tools through the NOVIS Transcarotid NPS.
- Rates of revascularization success assessed by angiographic core lab (mTICI \geq 2b)

To determine if the NOVIS NPS patients are comparable in safety to TCAR patients using the ENROUTE NPS, the following mutually exclusive populations will be compared:

Within the ***Complete NOVIS NPS Population***: All NOVIS NPS patients who were enrolled as part of the ITT study population in the NITE 1 study.

Within the ***Complete TCAR Population***: All TCAR patients who were enrolled in the ENROUTE clinical program (PROOF, and ROADSTER studies) and underwent the procedure.

There will be two independent sets of analyses performed to assess comparability between both patient populations – one using the ITT NITE 1 study population and the second using the Per Protocol NITE study population. The research questions, datasets, methods of analysis, and summarization of the results will be discussed in this SAP. The general design of the analysis summary tables, figures, and patient data listings used to present the analysis results are also presented in this plan.

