4. STATISTICAL RATIONALE FOR THE NITE 1 FEASIBILITY STUDY

The Intent-to-Treat (ITT) population is defined as enrolled patients who have consented, meet all inclusion and none of the exclusion criteria, and in whom transfemoral therapy has been deemed a failure. The per protocol (PP) population will be comprised of patients from the ITT population AND for whom no major protocol deviations have occurred. If the deviation meets any of the following criteria, it is considered a major protocol deviation:

- changing the protocol without prior IRB approval,
- failure to obtain informed consent, or
- falsifying research or medical records

The NITE 1 study protocol aims to recruit a minimum of 30 and a maximum of 40 patients in the PP population and to be analyzed in this study, unless the study enrollment is stopped sooner due to decision by the DSMB or Sponsor. Enrollment in the ITT cohort will cease when a targeted 30 PP patients have been accrued and complete the study follow-up period. Additional patients beyond 30 who are successfully enrolled while waiting for the 30th PP patient to complete the 90-day follow-up period, will be analyzed in the cohort for which they qualify, whether PP or ITT. Enrollment will continue till a maximum of 60 patients are enrolled in the ITT population or the study enrollment is stopped by decision from the DSMB or Sponsor.

Serious Adverse Events will be tabulated and reported accordingly. The primary endpoint and all secondary endpoints will be analyzed based on both the ITT and PP population. All available data on the ITT patients who enrolled in the study will be included.

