8. SAFETY

Safety will be assessed by the Data Safety Monitoring Board and events will be adjudicated for review by the Clinical Events Committee, as outlined in the NITE 1 protocol. For final analysis of the safety events, binary rates will be calculated using a denominator as the number of all subjects in the study regardless of their follow-up time.

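### The safety comparison sets all enrolled NITE 1 patients against TCAR patients who had the procedure, and no started-procedure set is defined for NITE 1

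*SAP*

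**What the plan says.** SAP section 2 names two populations for judging whether NOVIS patients are comparable in safety to TCAR patients. The NITE 1 population is "All NOVIS NPS patients who were enrolled as part of the ITT study population in the NITE 1 study". The TCAR population is "All TCAR patients who were enrolled in the ENROUTE clinical program (PROOF, and ROADSTER studies) and underwent the procedure". The comparison is to be run twice, once with NITE 1 ITT and once with NITE 1 PP.

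SAP section 4 defines ITT as enrolled patients who have consented, "meet all inclusion and none of the exclusion criteria, and in whom transfemoral therapy has been deemed a failure". PP is ITT minus patients with a major protocol deviation, and three kinds are listed: protocol changes without IRB approval, missing consent and falsified records. Protocol sections 14.1 and 22 agree, except that section 22 also has a general sentence about deviations affecting rights, safety or well-being.

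For the final safety analysis, SAP section 8 states that "binary rates will be calculated using a denominator as the number of all subjects in the study regardless of their follow-up time".

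Neither document defines a safety, as-treated or started-procedure set for NITE 1. The SAP's purpose statement does describe patients "who underwent endovascular treatment using the transcarotid approach with flow reversal in this initial feasibility (NITE 1) study", but this is not a population definition.

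**The concern.** Device-related serious adverse events are a primary outcome, and SAP section 5 compares them, permanent cranial nerve injury (CNI) and ancillary-device dissections numerically with TCAR experience. Such events require that the procedure was at least begun. A denominator that includes patients in whom it was not begun lowers the rate without any change in the hazard of the device. In a single-arm study, ITT is therefore not the cautious choice for device harm.

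The comparator carries a treatment condition and NITE 1 does not, so any dilution falls on one side only. The SAP says its planned analyses may go into regulatory submissions and manuscripts, so the two sides should be built by the same rule.

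**Working it through.** **Step 1: can an enrolled patient not start?** Protocol section 9 begins "A patient is considered enrolled after" and lists consent, eligibility and failed transfemoral therapy. Carotid access comes later. Protocol 10.3.3 says: "After completing confirmatory duplex ultrasound, access to the common carotid artery cephalad to the clavicle will be gained using surgical techniques". There is thus an interval between enrollment and neck incision, with at least one check in it.

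**Step 2: does either analysis set remove such a patient?**
- ITT: no. All its conditions are met before the neck incision.
- PP: no. Not starting is none of the three listed major deviations, and the general sentence in Protocol section 22 does not clearly reach it.
- SAP section 8: no. The denominator is all subjects.

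**Step 3: can such a patient contribute an event?** Not a device- or access-related one. Adverse event collection also begins at the index procedure (Protocol section 12).

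**Step 4: formula.** Let N be the number enrolled, k the number not started, x the number of events and u = k/N.

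Planned rate = x/N = [x/(N − k)] × (1 − u)

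Check with N = 30, k = 1, x = 2: 6.90% × 29/30 = 6.67% = 2/30.

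**Step 5: size.** The documents give N: 30 to 40 in PP and at most 60 in ITT (Protocol 14.2). They give no expected k or x. I assume x = 2 and let k vary.

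| N | Planned rate (x/N) | k = 1 | k = 2 | k = 3 | k = 6 |
|---|---|---|---|---|---|
| 30 | 6.7% | 6.9% | 7.1% | 7.4% | 8.3% |
| 40 | 5.0% | 5.1% | 5.3% | 5.4% | 5.9% |
| 60 | 3.3% | 3.4% | 3.4% | 3.5% | 3.7% |

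With k = 0 the two rates are identical. At N = 30 the shift is 0.2 points for k = 1 (6.90 − 6.67), 0.5 for k = 2 (7.14 − 6.67) and 1.7 for k = 6 (8.33 − 6.67).

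**Step 6: precision.** Exact (Clopper-Pearson) 95% limits for 2/30 are 0.8% to 22.1%, and for 2/29 they are 0.8% to 22.8%. With no events, the upper limit is 11.6% at n = 30, 11.9% at n = 29 and 12.3% at n = 28.

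The plan has no sample-size or power figure that depends on this point, so there is none to reproduce.

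**The case against.** The strongest reply is that the two sets may coincide in practice. Failed transfemoral therapy is already a condition of enrollment. Venous access and carotid diameter are inclusion criteria, and CT angiography precedes the procedure (Protocol 8.3 and 10.2.1). Sites must be able to change approach without moving the patient (18.1), and the study procedure is described as the only thrombectomy option left (23.6). Adverse events and follow-up are timed from the index procedure, as if every enrolled patient has one. The purpose statement and the label NOVIS NPS patients can also be read as meaning treated patients. In addition, the comparison is numerical, with no test (Protocol 14.3) and no margin, and the planned listings would allow a recount.

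Most of this stands as an argument about size. It does not settle the rule: neither phrase defines an analysis set, the ITT definition and SAP section 8 carry no treatment condition, and listings do not change the planned rates.

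A reader might infer more than the documents support:
- **Abandoned cases.** Protocol 10.3.4 says "The transcarotid intervention may be abandoned at the discretion of the treating operator". That sentence sits in the endovascular step, so it mainly describes patients who have already started. They belong in a started-procedure set and dilute nothing.
- **Aborted TCAR cases.** Protocol 3.2.4 excludes them from a mean incision-to-cannulation time. That says nothing about a safety denominator.
- **TCAR rates already on a reduced set.** The ROADSTER serious dissection and wound hematoma rates in Protocol 3.2.2 are 4/219 and 5/219, over the full stated trial size. Some ROADSTER 2 percentages imply fewer than 692 patients, but nothing shows that treatment status is the reason. SAP section 2 names only PROOF and ROADSTER.

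**Conclusion.** The point holds in a limited form. The two sides of the safety comparison are defined by different rules, and neither ITT nor PP removes a NITE 1 patient whose procedure never started. For device- and access-related events the effect can run only one way, towards a lower NITE 1 rate, by the factor (1 − u).

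Its size is unknown, probably small and possibly zero. At N = 30 with 2 assumed events, one or two such patients move the rate by 0.2 to 0.5 points, well inside an interval of 0.8% to 22.1%. The documents do not support saying that the comparison would be materially distorted or that ITT and PP should be replaced.

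The conclusion rests on two assumptions: that a patient who never starts cannot have these events, and that the treatment condition on the TCAR side is applied as written. It does not extend to 90-day mRS. Nor does it carry over cleanly to symptomatic intracranial hemorrhage (SICH), which the stroke itself can cause. This is worth correcting before analysis because the correction is cheap and the direction is known.

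**What to change.** In the SAP:

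- Define a NITE 1 safety set of all patients in whom the transcarotid procedure was started, for example from neck incision, including those abandoned after the start.
- Use it for the TCAR comparison of device-related serious adverse events, permanent CNI and ancillary-device dissections, alongside the ITT and PP tables that Protocol 14.3 requires.
- For the TCAR side, state the starting point that was applied and the resulting denominator. If this cannot be recovered, label the match approximate.
- Report the number enrolled but not started.
- Keep ITT for 90-day mRS and for the comparison of SICH with the stroke literature.

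Cost: SAP wording, one flag per patient from neck-incision times already collected (Protocol 7.2), and one more table set. No new patients or data are needed. The downsides are more tables to read and possibly slightly less favourable rates. If every enrolled patient starts, the rates do not change.

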3. OVERVIEW OF THE NOVIS TRANSCAROTID NPS SYSTEM

The Silk Road NOVIS Transcarotid NPS consists of four primary components:

- Transcarotid Arterial Sheath with Arterial Dilator
- Venous Return Sheath with Venous Dilator
- Flow Controller with Filter
- 0.035" Extra Support, J-Tip Guidewire

When assembled, the NOVIS Transcarotid NPS creates an arteriovenous shunt that can reverse the flow of blood in the carotid artery from antegrade to retrograde, shunting embolic particles away from the cerebral circulation during endovascular interventions. The NOVIS NPS is intended to provide vascular access and embolic protection during treatment with neurothrombectomy devices; it is not intended to aspirate the carotid artery and its branches or to perform mechanical neurothrombectomy at a distance from the site of occlusion. Device depictions and components are provided in the NITE 1 Clinical Protocol.

4. STATISTICAL RATIONALE FOR THE NITE 1 FEASIBILITY STUDY

The Intent-to-Treat (ITT) population is defined as enrolled patients who have consented, meet all inclusion and none of the exclusion criteria, and in whom transfemoral therapy has been deemed a failure. The per protocol (PP) population will be comprised of patients from the ITT population AND for whom no major protocol deviations have occurred. If the deviation meets any of the following criteria, it is considered a major protocol deviation:

- changing the protocol without prior IRB approval,
- failure to obtain informed consent, or
- falsifying research or medical records

The NITE 1 study protocol aims to recruit a minimum of 30 and a maximum of 40 patients in the PP population and to be analyzed in this study, unless the study enrollment is stopped sooner due to decision by the DSMB or Sponsor. Enrollment in the ITT cohort will cease when a targeted 30 PP patients have been accrued and complete the study follow-up period. Additional patients beyond 30 who are successfully enrolled while waiting for the 30th PP patient to complete the 90-day follow-up period, will be analyzed in the cohort for which they qualify, whether PP or ITT. Enrollment will continue till a maximum of 60 patients are enrolled in the ITT population or the study enrollment is stopped by decision from the DSMB or Sponsor.

Serious Adverse Events will be tabulated and reported accordingly. The primary endpoint and all secondary endpoints will be analyzed based on both the ITT and PP population. All available data on the ITT patients who enrolled in the study will be included.

5. REVIEW OF THE DATA RESULTS AND THE PROPOSED METHOD OF ANALYSIS

The data results have been broken down into 3 groups based on the primary endpoints outlined in the NITE 1 protocol, as listed below, and will be applied to both the ITT and PP population.

- Device-related Serious Adverse Events (SAEs) – vascular complications including dissection, pseudoaneurysm, hematoma, arteriovenous fistula, thrombus formation, embolization and any vascular complication that may be attributed to the device AND requires surgical repair, surgical wound revision, transfusion, etc.
- Other Serious Adverse Events – permanent CNI, new SICH and dissections related to ancillary devices.

- Functional independence measured at 90-day mRS (proportion with mRS score 0-2)

As listed above, the first data review will compare the incidence of the device-related SAEs from NITE 1 to the device-related SAEs collected across the body of TCAR evidence to date. This comparison group will include device-related SAEs from the ENROUTE NPS clinical program (e.g., PROOF and ROADSTER) representing a patient population spanning from feasibility to pivotal to post-market study settings. In addition, the incidence of permanent CNI and new SICH from the NITE 1 patient population will be compared to the same comparison group as well as reference data for AIS patients treated with mechanical thrombectomy and the natural history of AIS in those patients who have not received or have failed mechanical thrombectomy. The use of ENROUTE NPS clinical program data as a point of comparison for device-related SAEs and permanent CNI is based on the comparability of ENROUTE NPS and NOVIS NPS. Although each device is used for different patient populations, the surgical approach and set-up of each NPS device are equivalent. In regard to new symptomatic hemorrhage, the risk for this event can be attributed to two main causes: the risk due to cerebral reperfusion injury and the risk due to interventional or mechanical manipulation of the cerebral vasculature. The first applies to both ENROUTE NPS and NOVIS NPS, since any carotid revascularization comes with risk for cerebral reperfusion injury. The latter may be considered more specific to the AIS patient population. However, due to the increased risk for bleeding among patients treated with ENROUTE NPS due to required use of DAPT pre-procedure and systemic heparinization during the procedure to achieve an ACT of > 250, which is not applicable in the NOVIS NPS procedure for AIS patients, these risks can be considered to offset one another in each population. Therefore, the occurrence for SICH from ENROUTE NPS procedures can be compared to NOVIS NPS. Next, the incidence of dissections related to ancillary devices will be compared to the dissections related to the ancillary devices used commercially for ENROUTE and captured through post-market surveillance data. These numerical comparisons are summarized below with reference to the outcome, comparison group. Finally, the functional modified Rankin Score (mRS) at 90 days will be compared to the average functional independence score at 90 days (mRS 0-2) from the relevant studies included in the meta-analysis by Mokin M, et al in AIS patients treated with mechanical thrombectomy and the natural history of AIS in those patients who have not received or have failed mechanical thrombectomy. These data comparisons are summarized in Table 1 below:

Table 1. Summary of Planned Data Reviews for NITE 1

Outcome	Comparison Group
Device-related SAEs	Device-related SAEs from the ENROUTE NPS clinical program
Other SAEs: Permanent CNI	Permanent CNI from the ENROUTE NPS clinical program
Other SAEs: new symptomatic hemorrhage	New symptomatic hemorrhage from the ENROUTE NPS clinical program and from

	referenced literature in a similar patient population (e.g. San Román et al. ²)
Other SAEs: Dissections related to ancillary devices	Dissections from ENROUTE NPS clinical program
Functional independence at 90 days (proportion with mRS score 0-2)	Compared to the average mRS (0-2) score at 90 days from referenced literature in a similar patient population (e.g. Mokin et al. ¹)

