The secondary endpoints demonstrate that the device has a high rate of acute, technical and procedural success (99.3%, 99.3%, and 95.7% respectively) and low rate of serious access site complications (0.7%). Furthermore, the non-hierarchical rates of events for all death (1.4%) and all stroke (1.4%) are equivalent to the hierarchical event rates for death and stroke respectively, meaning that there were no stroke related deaths. There were no major or hemorrhagic strokes in the ITT population. There was one cardiac death (0.7%) and one death due to sequelae from respiratory failure (0.7%).

² Rates include ARChE¹, 2 and 3 respectively

³ Rates include randomized and non-randomized arms respectively

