3.2.5 Anticoagulation

Several studies have been conducted to evaluate the safety of intraprocedural anticoagulation in the acute ischemic stroke (AIS) patient population. A few representative studies are summarized below, which largely demonstrate no difference in functional outcomes and rates of symptomatic

intracranial hemorrhage (sICH) among patients who receive intraprocedural anticoagulation and those who do not.

The TREVO 2 trial (Winningham et al. 2018) evaluated 173 AIS patients who underwent clot retrieval using the Merci coil retriever and Trevo stent retriever. The mRS at 90-days was independently associated with patients who received a heparin bolus, and the rate of TICI 2b/3 reperfusion and intracranial hemorrhages were similar between those who received and did not receive intraprocedural heparin. Another study (Farook et al. 2016) stratified the use of intraprocedural heparin among 76 AIS patients with MCA M1- or ICA-T occlusion and found significantly lower rates of hemorrhage among the heparin group ($p=0.02$). Finally the MR CLEAN registry, a multi-center prospective registry(Van De Graaf et al. 2019), presented data on 1,488 patients with ICA, ICA-T, MCA-M1, MCA-M2, ACA-A1 or ACA-M2 occlusions demonstrating no significant difference among patients treated with intravenous heparin and those without in functional outcomes (adjusted common odds ratio, 1.17; 95% CI, 0.87–1.56), successful recanalization (adjusted odds ratio, 1.24; 95% CI, 0.89–1.71), sICH (adjusted odds ratio, 1.13; 95% CI, 0.65–1.99), or mortality (adjusted odds ratio, 0.95; 95% CI, 0.66–1.38). However, site level analysis showed sites that used heparin more often, also had better functional outcomes (adjusted common odds ratio, 1.07 per 10% more heparin, 95% CI, 1.01–1.13). On the other hand, a Chinese study (Yang et al. 2019), presented an analysis on 619/917 patients from the ANGEL registry, which showed an increased risk for sICH and embolization and lower functional independence with heparinization (9.3 vs. 5.1%, adjusted $p = 0.02$; 7.1 vs. 3.1%, adjusted $p = 0.04$, respectively), although recanalization rates, total ICH, and long-term mortality did not differ between the heparinized and non-heparinized groups (adjusted $p > 0.05$ for all). In conclusion, the summary of these multiple data sets demonstrates comparable outcomes among patients who do and do not receive intraprocedural anticoagulation across functional outcome, sICH, and mortality.

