As a result, the sponsor does not believe patients are at any additional risk based on who has or has not received anti-coagulants during the procedure. With the exception of the required use of the pressurized, heparinized saline bag in section 10.3.3, the use of procedural anticoagulation has been carefully considered and will be left to the discretion of the operator.

4 Investigational Study Plan

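### The SAP accepts ENROUTE as a benchmark for symptomatic intracranial hemorrhage on an unsourced claim that bleeding risks offset, which the protocol's own figures do not support

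*SAP*

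**What the plan says.** SAP section 5 names two sources of new symptomatic hemorrhage: reperfusion injury, which it assigns to both devices, and manipulation of the cerebral vessels, which it allows may be more specific to AIS patients. Against the second it sets a higher bleeding risk with ENROUTE "due to required use of DAPT pre-procedure and systemic heparinization during the procedure to achieve an ACT of > 250". It says of this regimen and its consequence: "which is not applicable in the NOVIS NPS procedure for AIS patients, these risks can be considered to offset one another in each population". From that it concludes that ENROUTE SICH can be compared with NOVIS SICH. The matching row of SAP Table 1 reads "New symptomatic hemorrhage from the ENROUTE NPS clinical program and from" referenced literature in a similar patient population.

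The protocol bears on this in four places.

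- Section 3.2.5: apart from the required heparinized saline bag, "the use of procedural anticoagulation has been carefully considered and will be left to the discretion of the operator". The section reviews four heparin studies and concludes that SICH is comparable with and without intraprocedural anticoagulation.
- Section 10.3.3: at device set-up "a pressurized, heparinized saline drip is connected to the 3-way stopcock on the side arm of the rotating hemostasis valve".
- Section 23.2: anticoagulation is not required in NITE 1, and study patients are unlikely to be on DAPT.
- Section 3.2.2: ROADSTER patients had DAPT and anticoagulation to an ACT of at least 250 seconds, and "There were no major or hemorrhagic strokes in the ITT population".

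**The concern.** The ENROUTE comparison for SICH depends on the offset. For it to hold, AIS thrombectomy patients without the ENROUTE regimen must bleed about as often as carotid-stenting patients with it. The SAP gives no rate, ratio or citation for that, and the protocol contains figures that can be set against it.

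The argument also sits badly with protocol section 3.2.5. The SAP needs antithrombotic exposure to raise SICH enough to cancel an AIS-specific risk, whereas the protocol concludes that intraprocedural anticoagulation makes no difference to SICH in AIS. The populations differ, but the SAP does not address the tension.

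At stake is how a primary safety component is read. Against a rate near zero, the usual bleeding of thrombectomy could look like a device problem. Conversely, a low count could be credited as comparability with TCAR on an argument that nobody has shown.

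**Working it through.** The plan states no figure for the offset, so there is none to reproduce. The check asks whether the protocol's figures fit it.

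**Inputs**

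- ROADSTER ITT: 0 hemorrhagic strokes (protocol 3.2.2). The denominator is not printed. The printed rates 0.7%, 1.4%, 99.3% and 95.7% are jointly possible only for n = 138 to 141 (for example 1/141 = 0.7%, 2/141 = 1.4%, 140/141 = 99.3%, 135/141 = 95.7%). The combined ROADSTER population is 219.
- ROADSTER 2: stroke or death of any type 0.8% (protocol 3.2.3).
- Thrombectomy registry with 619 of 917 patients analyzed: SICH 9.3% with heparin and 5.1% without (protocol 3.2.5). The sentence lists three outcomes and two pairs of figures. Taken in order, the first pair is SICH. Arm sizes are not given.
- NITE 1: 30 to 40 per-protocol patients and at most 60 ITT (protocol 14.2).

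**Step 1. How high could the ENROUTE rate be?** With 0 events the two-sided 95% Clopper-Pearson upper limit is 1 − 0.025^(1/n).

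- n = 138: 2.6%
- n = 141: 2.6%
- n = 219 (assuming no events there either): 1.7%

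**Step 2. Does this fit the offset?** The no-heparin registry rate is 5.1/2.6 = about 2 times the upper limit, and 5.1/0.8 = about 6 times the ROADSTER 2 rate for any stroke or death. If the ENROUTE rate were 5.1%, the chance of 0 events in 141 would be 0.949^141 = 0.0006.

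The 5.1% has its own uncertainty. For an assumed no-heparin arm of 100 (5 events) its 95% interval is 1.6% to 11.3%. For 500 (26 events) it is 3.4% to 7.5%. Fisher's exact p against 0/141 runs from 0.012 to 0.003 over these sizes.

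**Step 3. What would NITE 1 show?** Expected events = n × p, and P(at least one) = 1 − (1 − p)^n.

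| n | Expected at 5.1% | P(≥1) at 5.1% | P(≥1) at 0.8% | One event as % |
|---|---|---|---|---|
| 30 | 1.53 | 79% | 21% | 3.3% |
| 40 | 2.04 | 88% | 27% | 2.5% |
| 60 | 3.06 | 96% | 38% | 1.7% |

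At n = 30, moving p across the interval for an assumed arm of 100 gives a chance of at least one event from 38% (p = 1.6%) to 97% (p = 11.3%). For an assumed arm of 500 it runs from 65% (p = 3.4%) to 90% (p = 7.5%).

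One event in 30 exceeds ROADSTER's zero and its 2.6% limit, and ROADSTER 2's 0.8%. One event in 40 or 60 exceeds the observed zero and the 0.8%, but not the 2.6% limit. The exact interval for 1/30 is 0.1% to 17.2%, so a single event says little about the true rate whichever benchmark is used.

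**The case against.** Much can be said for the plan, and several stronger readings fail.

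- **A reader might infer that the SAP calls heparin as such not applicable, against the protocol.** It does not. What it calls not applicable is required DAPT with systemic heparinization to an ACT above 250, and protocol section 23.2 agrees that anticoagulation is not required and DAPT is unlikely. The saline drip is a flush through the hemostasis valve, and nothing in the documents equates it with heparinization to a target ACT. What stands is narrower: heparin is permitted at the operator's discretion, so the SAP cannot assume that no NITE 1 patient receives it.
- **A reader might infer that ENROUTE is the only yardstick.** SAP section 5 and Table 1 both add AIS reference data for SICH. An ordinary thrombectomy rate would be shown beside a suitable comparator as well as an unsuitable one.
- **A reader might infer a wrong error rate or a wrong decision.** Protocol section 14.3 tests no hypothesis, and the SAP compares numerically, with no margin or success rule for SICH. The DSMB stopping rules are in a charter outside these documents.
- **A reader might take 9.3% as the rate under heparin and expect a heparin-driven excess to be read as a device effect.** That figure comes from the one dissenting study. The same section cites a larger registry with an adjusted odds ratio for SICH of 1.13 (0.65 to 1.99), a trial with similar hemorrhage rates, and a study with fewer hemorrhages under heparin. The documents do not establish such an excess, and this point does not need one: it rests on the no-heparin rate.

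The objection that the figures are not like for like also stands, and it limits the verdict.

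**Conclusion.** The offset is unsupported, and the protocol's figures point against it. They do not prove it false. The documents give about 5.1% SICH in thrombectomy without heparin, against 0 hemorrhagic strokes (upper limit 1.7% to 2.6%) in carotid stenting with DAPT and heparin. If NITE 1 has the 5.1% rate, at least one SICH is likely (79% to 96% for 30 to 60 patients) but not certain: the chance of none is 21% at 30 and 4% at 60.

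This rests on the following.

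- The figures come from different studies and populations.
- Hemorrhagic stroke in ROADSTER is not SICH as defined in protocol Appendix 4.
- The ROADSTER ITT denominator is inferred.
- Registry arm sizes and IV tPA use are not given, and NITE 1 excludes IV tPA.
- No PROOF hemorrhage data appear, so the pooled ENROUTE benchmark is unknown.
- The 0.8% in ROADSTER 2 is no strict ceiling. One death printed as 0.2% implies fewer than the 692 enrolled (1/692 = 0.14%, which rounds to 0.1%).

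The consequence is a misleading descriptive benchmark for one component of a primary outcome. It is worth correcting before analysis, and it is no ground for doubting the other ENROUTE comparisons.

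**What to change.** In SAP section 5, delete the offset argument and the conclusion drawn from it. In the new symptomatic hemorrhage row of Table 1, make the AIS-thrombectomy reference already listed there the benchmark, and either drop ENROUTE or label it context only. Keep ENROUTE for device-related SAEs and permanent cranial nerve injury, which the SAP justifies separately by the equivalent surgical approach and set-up.

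Reconcile the SAP's wording on antithrombotic exposure with protocol sections 3.2.5, 10.3.3 and 23.2, so that it says that procedural anticoagulation is not required but is left to the operator. No change to heparin use is proposed.

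Optionally, list procedural heparin for each SICH case. Protocol section 10.3.1 already has pertinent medication recorded by procedural step on the Concomitant Medication Form. With about two events expected, such a listing is descriptive and cannot separate a heparin effect from a device effect.

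The cost is SAP wording and, at most, one comparator fewer for one component.
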